Eligible subjects will be sequentially assigned to one of two Cohorts (A or B) using a time-lagged dose escalation methodology as illustrated in Figure 3-2 below.

Figure 3-2 TCD601B102 Treatment Regimen

Background Immunosuppression (TAC/MMF/CS) will be administered with each treatment arm

Within each Cohort, it is planned that 12 subjects will be randomized between siplizumab (at two dose levels, increasing per Cohort as above) or rATG control, in an 8:4 ratio prior to renal transplantation on Study Day 0, as outlined in Table 3-1.

Table 3-1 **Dosing Regimen** 

Cohort	Arm	Subjects (n)	Product	Dosing Regimen
Cohort A	Arm 1	8	Siplizumab	0.2 mg/kg (Days 0 and 4)
	Arm 3	4	rATG	1.5 mg/kg (Day 0, 1 and 2)
Cohort B	Arm 2	8	Siplizumab	0.6 mg/kg (Days 0 and 4)
	Arm 3	4	rATG	1.5 mg/kg (Day 0, 1 and 2)

Subjects randomized to receive siplizumab will receive two intravenous (IV) doses on Days 0 and Day 4 post-transplant. The first dose will be administered intravenously, peri-operatively and must be completed prior to revascularization and perfusion of the allograft. The second and final dose of siplizumab will be administered intravenously on Day 4 post-transplant (Study Day 4). Subjects

randomized to the rATG control arm (Arm 3) will receive three intravenous (IV) doses of 1.5 mg/kg on Days 0, 1 and 2, regardless of Cohort assignment.

Siplizumab and rATG will be combined with concentration-controlled TAC (BID) dosing to a whole blood trough concentration 4-11 ng/mL, and MMF or equivalent (BID), and should be started within 24 hours post-transplant. Subjects will also receive CS per local practice with a minimum of 5.0 mg/d prednisone or equivalent until Month 12.

Dose escalation from one Cohort to the next will be determined 28 days following the last investigational product administration in the 4th siplizumab treated subject in each treatment Cohort and prior to dose escalation to the subsequent Cohort, a review of all available safety, tolerability and PD data will be conducted by ITB-MED in collaboration with the Investigators. This 28-day safety period allows sufficient time for subjects to reach full-receptor occupancy, maximum pharmacodynamic activity, and for the presentation of acute, drug related toxicities.

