In the event there is no evidence of acute, dose limiting toxicity (DLT), randomization to the next dose level may be initiated. Alternatively, a decision to terminate the dosing arm could be reached. It is also possible for additional and/or intermediate dose level to be added during the course of the study per amendment (See Section 13.4.4). Cohorts may be added at any dose level below the maximum tolerated dose in order to better understand safety, PK or PD.

This escalation data review will be repeated prior to dose escalation/termination decisions for each Cohort. The review of subject data and dose escalation may occur before all subjects have been randomized to a given Cohort. If the next dose level is opened to subject assignment, Cohorts will be back filled to achieve a final sample size of 12 subjects.

Dose escalation will be based on a priori defined criteria outlined in Section 6.2.8.

In addition to the review of data for dose decision purposes as noted above, an independent Data Monitoring Committee (DMC) will conduct an ongoing review of cumulative PK, PD, safety, Adverse Events (AEs) and Serious Adverse Event (SAE) data as well as EBV-viral load and PTLD surveillance results, including clinically relevant changes on physical exam and clinical laboratory assessments and ad hoc imaging. The Committee will convene on a quarterly basis or as described in the DMC Charter. If at any time the observed AEs meet or exceed the a priori-defined stopping criteria, the study will be placed on hold pending a review as outlined in Section 9.1.1.

Additionally, a formal interim analysis will occur once 50% of subjects assigned to the treatment Cohorts complete their 6-month study assessment.

This formal interim analysis will be conducted to assess the safety/tolerability (e.g., AEs, SAEs, clinical laboratory assessments, vital signs, PK data and PK/PD activity (e.g., immunophenotyping and CD2 receptor occupancy). The analysis will also include assessment of biopsy proven acute rejection (BPAR), graft losses deaths, and key safety endpoints. In the event the acute rejection rate exceeds a clinically relevant threshold set forth in the protocol and DMC charter, or the a priori defined stopping rules, enrollment will be suspended to allow for the early termination of any treatment cohort where the benefit/risk of siplizumab is deemed unacceptable.

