#### 4.5 **Risks and Benefits**

The risks and benefits are expected to be broadly similar to that of ATG in combination with SoC immunosuppression. In particular, the risk of increased infections and first dose effect, will be minimized by adherence to the inclusion/exclusion criteria, premedication, close clinical monitoring and minimization of protracted siplizumab exposure during treatment period. Infection risk will be mitigated by following applicable national vaccination guidelines and by use of prophylaxis (See Section 6.5). Similarly, the risks of SARS-CoV-2 will be minimized by following local, national and international guidelines for immunosuppressed and solid organ transplant patients (See Section 4.5.3).

The risks of insufficient efficacy (higher rate of acute rejection-tBPAR than SoC) will be minimized by enrolling a moderate immunologic risk patient population, frequent monitoring of clinical labs and signs and symptoms suggesting BPAR and the early discontinuation of any treatment arm that is unsafe or ineffective according to the Stopping Rules detailed in Section 9.1.1.

The below sections list the possible risks related to siplizumab treatment. For further details please refer to Section 7 of the current IB.

Information and guidance for the SoC treatment used in this study is provided in the local labelling information and should be strictly followed.

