#### 8.4.7 **Renal Biopsy**

Any biopsies performed according to local practice must be recorded. Biopsies will be read by the local pathologist according to local practice and the 2017 Banff criteria (Appendix 7). The results of the biopsy read by the local pathologist will be listed on the applicable eCRF.

Additionally, for all suspected rejection episodes, regardless of initiation of anti-rejection treatment, a renal biopsy must be performed within 48 hrs. The results will be used for subject management for acute rejection.

Please refer to the Laboratory Manual for details on biopsy handling and histology assessments.

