# 8.7 Exploratory Biomarker Assessments

# 9 Study Discontinuation and Completion

### 9.1 Discontinuation

## 9.1.1 Safety Stopping Rules

The following stopping rules based on potential toxicities will serve as the basis for placing enrollment and dose escalation on hold.

Although the stopping criteria do not incorporate an absolute requirement for causality, the potential relationship between an AE(s) and siplizumab will be evaluated carefully on a case-by-case basis between ITB-MED and the Investigator. Following a review of the AE(s), a decision to permanently discontinue enrollment or re-initiate dosing will be made by the DMC. Dose limiting toxicities (DLTs) will be assessed according to the standardized toxicity grading scale, the National Cancer Institute (NCI) CTCAE version 5.0 (NCI 2017).

- One (1) subject death or graft loss within the first month with the exception of technical failures.
- One (1) subject presents with histologically\* confirmed EBV-PTLD.
- One (1) subject with Grade 3 or higher cytokine release syndrome within 24 hours of any siplizumab administration.
- One (1) subject with any Grade 4 toxicity, considered drug related as determined by the Investigator within the first 28 days.

- Two (2) subjects with sustained (>7 days) Grade 3 neutropenia (neutrophil counts 200/mm3 to < 500 to; 0.2 to <0.5 x 10e9/L) considered related to siplizumab.
- Two (2) or more subjects presenting with Grade 3 or higher toxicity considered drug related as determined by the Investigator, including infusion reactions, within 24 hours of any siplizumab administration.
- Three (3) or more subjects per cohort presenting with Grade IIA or higher BPAR (T-cell mediated rejection (TCMR); central pathology) during the first 6 months post-transplant.

\*NOTE: in the case of suspected PTLD lesions where a biopsy is not possible (e.g., CNS symptoms), radiographic and imaging (MRI) studies may be used to stage and assess the disease.

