#### 9.3 Subject Replacement

### Replacement during Dose Escalation

Subjects will not be replaced on study. However, if a subject is considered as non-evaluable, enrollment of a new subject to the current cohort will be considered if there is less than the required number of evaluable subjects. Enrollment of new subjects may be considered until at least the minimum number (4) or at most the maximum number (8) of evaluable subjects is achieved within the cohort.

Minimum and maximum numbers of evaluable subjects per cohort are defined in the guidelines for dose escalation and determination section.

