# Schedule of Assessments

### Footnotes

SCR = screening min = minute EOS/ET = end of study or early termination SD = noted in source document EOW = every other week Month = 28 days

☐ = Eligibility must also be confirmed on Day 0 prior to randomization

(a) all screening procedures may occur on the day of transplant for deceased donors

(b) vitals collected pre-dose, immediately following the end of the infusion, and 6 hours after completion of infusion with siplizumab or rATG. Other timepoints captured as indicated. Weight is captured pre-dose on Days 0 and 4 for siplizumab treated subjects and pre-dose on Days 0, 1 and 2 for rATG treated subjects.

(c) results obtained within the past 6 months acceptable; PRA when available

(d) results obtained within the past 12 months are acceptable for the initial assessment of EBV (donor and recipient) and CMV. Serological testing for BKV is not required at Screening. EBV, CMV and BKV viral testing via PCR should be conducted thereafter

(e) daily while in hospital and then as noted above; see protocol for panel analytes

(f) a negative pregnancy test must be available prior to randomization (for females of child bearing potential)

(g) DSA collected as noted above and additional collection with each kidney biopsy

(h) tacrolimus trough concentrations on days 0, 1, 7, 14, 21, 28; on months 3, 6, 12, and as clinically indicated. Sample Collection should be taken before the next dose is administered

(i) Randomization:

Subjects randomized to siplizumab: first dose administered pre-or intra-operatively and timed so that completion of the infusion is no earlier than 4 hours prior to revascularization and perfusion of the allograft. The Day 4 dose should be administered between 0800 and 1000 to faciliate future sample collection/visits.

Subjects randomized to rATG (Control): administration will occur on Day 0, Day 1 and Day 2 per SoC.

(j) must be started within 24 hours post-transplantion

(k) prophylaxis per local medical practice

(L) pre-implantation biopsy on Day 0; for-cause and/or protocol biopsies as indicated per local practice

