#### 4.2.2. Dose Escalation Criteria

##### **TCD601B102**

Twenty-eight days following the last investigational product administration in the 4th Sipilizumab-treated subject in each treatment Cohort and prior to dose escalation to the subsequent Cohort, a review of all available safety, tolerability and PD data will be conducted by ITB-MED in collaboration with the Investigators. This 28-day safety period allows sufficient time for subjects to reach full-receptor occupancy, maximum pharmacodynamic activity, and for the presentation of acute, drug related toxicities.

In the event there is no evidence of acute, dose limiting toxicity (DLT), randomization to the next dose level may be initiated. Alternatively, a decision to terminate the dosing arm could be reached. It is also possible for additional and/or intermediate dose levels to be added during the course of the study per amendment. Cohorts may be added at any dose level below the maximum tolerated dose in order to better understand safety, PK or PD.

This escalation data review will occur prior to dose escalation/termination decisions for each Cohort. The review of subject data and dose escalation may occur before all subjects have been randomized to a given Cohort. If the next dose level is opened to subject assignment, Cohorts will be back filled to achieve a final sample size of 10 subjects.

In addition to the review of data for dose decision purposes as noted above, an independent Data Monitoring Committee (DMC) will conduct an ongoing review of cumulative PK, PD and safety, Adverse Events (AEs) and Serious Adverse Event (SAE) data. The Committee will convene on a quarterly basis or as described in the DMC Charter. If at any time the observed AEs meet or exceed the a priori-defined stopping criteria, the study will be placed on hold pending a review.

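### The only printed rejection stopping rule counts rATG control rejections toward a hold on siplizumab and relies on a central grade whose path is not described; the SAP then reports only treated rejection

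*Protocol*

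**What the plan says.** **The rule.** Protocol 9.1.1 pauses enrollment and dose escalation if there are "Three (3) or more subjects per cohort presenting with Grade IIA or higher BPAR (T-cell mediated rejection (TCMR); central pathology") during the first 6 months after transplant. The synopsis and SAP 4.2.3 repeat it. Protocol 4.5 relies on these rules to limit the risk of a higher rejection rate than standard of care, through "the early discontinuation of any treatment arm that is unsafe or ineffective according to the Stopping Rules detailed in Section 9.1.1". Section 9.1.1 also mentions a rejection-rate threshold in the protocol and the DMC charter, but the protocol prints no other rejection number.

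**The cohort.** Protocol 3.1: "Within each Cohort, it is planned that 12 subjects will be randomized between siplizumab" and rATG, 8:4, and "Cohorts will be back filled to achieve a final sample size of 12 subjects". Table 6-1 agrees. Protocol 9.3, on replacement during escalation, allows enrollment until "at most the maximum number (8) of evaluable subjects is achieved within the cohort". SAP 4.2.2 instead says "Cohorts will be back filled to achieve a final sample size of 10 subjects".

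**The read.** Protocol 8.4.7 has the local pathologist read the biopsies: "The results of the biopsy read by the local pathologist will be listed on the applicable eCRF". It refers to the Laboratory Manual for histology details. Footnote L of the Schedule of Assessments gives "for-cause and/or protocol biopsies as indicated per local practice".

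**The endpoint.** Protocol Table 2-1 has tBPAR as the objective and incidence of BPAR in the endpoint column. SAP 4.1 and 11.5 carry only tBPAR, defined as anti-rejection treatment plus Banff histology with borderline changes included. SAP 11.5 does not say whose read is used.

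**The concern.** The hold exists to decide whether siplizumab's benefit/risk at a dose is acceptable; 9.1.1 says so when it describes ending a cohort early. A rejection in an rATG subject is not evidence on that question, yet it adds to the count. Three other rules in the same list refer expressly to siplizumab, either as the drug given or as the suspected cause. This one does not.

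The rule also uses a central grade, but the only result with a described path to the database is the local one. Neither document says when a central grade is due or what happens while it is pending, although 9.1.1 promises near real-time review of rejection.

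In the final analysis, a biopsy-proven rejection that was not treated is not counted in any planned table. Treatment is decided by an investigator who knows the arm, and Protocol 4 acknowledges that investigator bias can affect management in an open-label study. With 8 subjects per dose, one case is 1/8 = 12.5 percentage points.

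**Working it through.** The documents give no operating characteristics for the rule, so there is no planned figure to reproduce.

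**Inputs.** 8 siplizumab and 4 rATG subjects per cohort and a threshold of 3 (Protocol 3.1 and 9.1.1). Rejection rates of 7-8% at one year under current care (Protocol 1.1) and 12.4% and 13.3% at 12 months without induction (Protocol 4). These are rates for any rejection over 12 months. No rate is given for Grade IIA or higher at 6 months, so using them treats every rejection as qualifying and is an upper case. The 5%, 25% and 4% rates below are assumptions.

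**Formulas.** Let p be the siplizumab rate and q the rATG rate, with subjects independent.

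- Siplizumab-only count: P8 = P(Bin(8,p) ≥ 3).
- Whole-cohort count, as the rule is worded: P12 = P(Bin(8,p) + Bin(4,q) ≥ 3).
- The whole-cohort count can only add cases, so the two disagree with probability P12 − P8.

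**Worked case, p = q = 0.07.**

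- P8 = 1 − [0.93^8 + 8(0.07)(0.93^7) + 28(0.07²)(0.93^6)] = 1 − (0.5596 + 0.3370 + 0.0888) = 0.0147.
- P12 = 1 − [0.93^12 + 12(0.07)(0.93^11) + 66(0.07²)(0.93^10)] = 1 − (0.4186 + 0.3781 + 0.1565) = 0.0468.

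| p (siplizumab) | q (rATG) | P8 | P12 | Disagree |
|---|---|---|---|---|
| 5% | 5% | 0.6% | 2.0% | 1.4% |
| 7% | 7% | 1.5% | 4.7% | 3.2% |
| 8% | 8% | 2.1% | 6.5% | 4.4% |
| 12.4% | 7% | 6.6% | 12.6% | 6.0% |
| 13.3% | 8% | 7.9% | 15.2% | 7.4% |
| 25% | 4% | 32.2% | 37.1% | 4.9% |
| 25% | 8% | 32.2% | 41.9% | 9.8% |

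When the arms have the same low rate, the wording roughly triples the chance of a hold: 4.7/1.5 and 6.5/2.1 are both about 3.1. Over the four unequal-rate rows the two counts disagree in 4.9-9.8% of cohorts.

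**The read.** No arithmetic applies. Section 9.1.1 asks for a central grade; 8.4.7 supplies a local one; the step between them is in neither document.

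**The endpoint.** Protocol 6.7.1 requires every acute rejection episode to be entered on the eCRF, treated or not. The data for a table regardless of treatment are therefore already collected.

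**The case against.** The strongest reply is that the rule is defined. The synopsis, Protocol 3.1 and 6.1 and the SAP design section all make a cohort 12 subjects, and the smaller group is called an arm. A reader might infer from the 8 in Protocol 9.3 that the term has no settled meaning. The documents do not support that: the 8 is a ceiling on evaluable subjects for replacement. This stands, and it is why the literal count includes controls. The SAP's 10 is a discrepancy to correct, not a rival definition.

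A hold is also not a termination. Cases are reviewed for causality and the DMC decides, so an rATG case would be seen for what it is. That limits the harm of a spurious hold but does not justify a trigger that includes controls.

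On the read, a reader might infer that no central read exists, or that a hold is lost whenever the central reader does not confirm a local grade. Neither follows. The Laboratory Manual may arrange the central read, and central results need not pass through a site eCRF. A local grade that is not confirmed centrally is the rule working as written. What remains is that the protocol and SAP give no timing or interim action.

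On the endpoint, the SAP matches the stated secondary objective, rejections are expected to be treated, the interim analysis assessed BPAR, and CRF data will be listed. A reader might infer that reader disagreement on grade would move the tBPAR rate. In general it would not, because borderline cases count: a treated case downgraded from IIA to IA, or from IA to borderline, stays in. Only a change to or from no rejection matters, and the documents give no figure for that.

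**Conclusion.** The concern holds in a limited form. As worded, control rejections count toward a hold on siplizumab. At 7-8% in both groups this raises the chance of a hold per cohort from 1.5-2.1% to 4.7-6.5%. The two counts disagree in about 5-10% of cohorts in the unequal-rate scenarios and in 1.4% at 5% in both arms. These figures rest on assumed rates, independent subjects and full cohorts; with rates specific to Grade IIA or higher at 6 months they could be lower.

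The dependence on a central grade with no described path is a gap in the two supplied documents, which the Laboratory Manual or the DMC charter may close. The absence of a table for rejection regardless of treatment is a reporting gap against the endpoint column of Table 2-1.

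The trial is descriptive, so no error rate or power is affected. Nothing here shows that an ineffective dose would be allowed to continue. This is worth changing, but it is not a fault that undermines the study.

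**What to change.** 1. In Protocol 9.1.1, the synopsis and SAP 4.2.3, count three or more siplizumab-treated subjects at one dose level, and show rATG cases beside the count. The downside is fewer holds: at 12.4% and 7%, the chance falls from 12.6% to 6.6% per cohort.
2. Let a local Grade IIA or higher grade trigger a provisional hold, confirmed or lifted by the central read that the rule already requires. The cost is an occasional hold that is later lifted.
3. In SAP 11.5, add biopsy-proven rejection regardless of treatment, by arm, with borderline separate from Grade IA and above and with the Clopper-Pearson intervals of SAP 8. State which read is used. This is one table from data already collected.
4. Correct 10 subjects in SAP 4.2.2 to 12.

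If enrollment is complete, items 1 and 2 can no longer change conduct. The study report should then state whether the rule was met under each count and each available read.

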# 9.1.2 Discontinuation of Study Treatment

Discontinuation of study treatment for a subject occurs when study treatment is stopped earlier than the protocol planned duration. Discontinuation can be initiated by the subject, the investigator, or by ITB-MED.

Possible reasons for study treatment discontinuation are:

- AE, e.g., cytokine release syndrome, PTLD, CTS
- Lack of Efficacy
- Technical problem during transplant surgery
- Primary non-function
- Subject/Guardian Decision
- Lost to follow-up
- Pregnancy
- Death
- Graft Loss

The Investigator should discontinue a subject from their randomized treatment regimen if he/she believes that continuation in the study would be detrimental to the subject's well-being.

Subjects who discontinue their study treatment should NOT be considered withdrawn from the study UNLESS they withdraw their consent to participating in all the elements of the study. Such subjects should remain in the study, if possible, and receive standard of care immunosuppression, according to local practice, and return for follow-up visits through Month 12.

All randomized subjects are expected to continue in the study up to Month 12. If they refuse to return for these assessments or are unable to do so, every effort should be made to contact them to

determine their health status, evaluate safety (SAEs) and to request a final study visit. Documentation of attempts to contact the subject should be recorded in the source documentation. If the subject is unable to return for a final study visit, every effort to obtain the subject and graft status should be made and documented within the subject chart.

### 9.1.3 Withdrawal of Informed Consent

Subjects may voluntarily withdraw consent to participate in the study for any reason at any time. Withdrawal of consent occurs only when a subject no longer wishes to participate in the study and does not allow further collection of personal data.

In this situation, the investigator should make a reasonable effort (e.g., telephone, e-mail, letter) to understand the primary reason for the subject's decision to withdraw his/her consent and record this information. Study treatment must be discontinued, and no further assessments completed. Further attempts to contact the subject are not allowed unless safety findings require communicating or follow-up.

ITB-MED will continue to maintain, and use collected study information (including any data resulting from the analysis of a subject's samples until the time of withdrawal) according to applicable law.

All biological samples collected at the time of withdrawal, but not yet analyzed for subjects enrolled within the US, may still be used for further testing/analysis in accordance with the terms of this protocol and of the ICF.

